9.5 STUDY SIZE

There will be around 4,000 patients using Tio+Olo in the Taiwan NHIRD that can be enrolled in this study.

Assuming that observed incidence rates of each AE from Ferguson paper could be replicated, and 4000 patients were enrolled in the study in a uniform distribution from 0 to 6 years. The estimation and 95% CI for incidence rate of each AE among new users of Spiolto® Respimat® for the study duration of 6 years were calculated based on Poisson distribution and provided as the following table.

Table 1 Incidence rate of AEs

Adverse events	Incidence	N	95% CI	
	rate per		Lower	Upper
	100			
	patient			
	years			
Pneumonia	4.69	4000	4.308	5.083
COPD	55.42	4000	54.092	56.758
exacerbation				
Arrhythmia	1.82	4000	1.583	2.067
Supraventricul	1.16	4000	0.975	1.358
ar tachycardia				

001-MCS-90-118_RD-23 (2.0) / Saved on: 03 Jul 2020

NIS Protocol Page 25 of 43 BI Study Number: 1237-0109 c38644780-01

Proprietary confidential information © 2022 Boehringer Ingelheim International GmbH or one or more of its affiliated companies

Incidence rate of AEs from Ref: G.T. Ferguson, et al., Respiratory Medicine 143 (2018) 67–73.

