	In Taiwan, the population-based cancer registry was founded in 1979. Since then, the registry collected basic information, referred to the "20 items short-form system," on incident cancer cases (including cancer-		
	in-situ) within one year after the initial diagnosis from hospitals with more than 50-bed capacity throughout the country. Recorded items include date of birth, gender, time and method of diagnosis, cancer site and morphology, treatment summary and death. From 2002		
	onward, a "long-form" system was established to collect more detailed information of cancer staging, treatment and follow-up data		
	from hospitals with more than 500 new cancer cases diagnosed		
	annually. The number of recorded items increased from 20 to 65 in		
	2002, further to 95 in 2007, and to 114 in 2011. In 2003, Cancer Control Act was introduced with all reporting hospitals mandated to		
		•	cancer registry. To ensure
	-		g the quality of cancer
			Registry was established in
	2006, conducting	random medical record	d review to ensure data
	for this study.	10. TCR data from 200	00 through 2018 will be used
Study size:	There will be arou	and 4.000 patients usin	g Tio+Olo in the Taiwan
		e enrolled in this study	C
	 		,
	The following table provides an estimation and 95% CI for incidence rate of each AE among new users of Spiolto® Respimat® for the study		

NIS Protocol Page 15 of 43 BI Study Number: 1237-0109 c38644780-01

Name of company:						
Boehringer Ingelhei	m					
Name of finished m	nedicinal					
product:						
Spiolto Respimat						
Name of active ingi	redient:					
Tiotropium + Oloda	terol {R03AL06}					
Protocol date:	Study	Version/Revision	on:	Vers	ion/Revisio	on date:
11 May 2022	number:					
	1237.0109	1.0		NA		
	duration of 6 years.					
	Adverse	Inciden	N		95% CI	
	events	ce rates	111	-	Lowe	Uppe
	o v onts	per 100			r	r
		patient			•	
		years				
	Pneumonia	4.69	400		4.308	5.083
			0			
	COPD	55.42	400		54.09	56.75
	exacerbation		0		2	8
	Arrhythmia	1.82	400		1.583	2.067
	G	1.16	0		0.075	1.250
	Supraventricul ar tachycardia	1.10	400		0.975	1.358
Data analysis	-	1:4: 4 -1		1.	1'	1
Data analysis:	All variables, incl			iics, b	aseline mea	sures, and
	outcomes, will be	•	•		- .	
	We will first descr			•		
	characteristics at b				=	=
	statistics. For the a	•	-			
	AEs during entire		will be	calcu	lated based	on the
	following formula	:				
	(Total number of	patients in the Ti	o+Olo c	cohort	experienci	ng an

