9.7.1 Main analysis

All variables, including patient characteristics, baseline measures, and outcomes, will be analysed descriptively.

- For all analyses, variables will be reported as follows: Continuous variables (e.g., age) will be presented as means (with standard deviation, SD) and/or medians (with interquartile range, IQR), minimum, maximum.
- Categorical variables (e.g., sex) will be presented as absolute and relative frequencies.

We will first describe formation of the study cohort. Patient characteristics at baseline will be described using standard descriptive statistics. Absolute standardized differences (ASDs) will be used to compare the characteristics between the two groups, in which a >0.1 ASD indicates a meaningful difference.

As an objective of the study was to compare the clinical attributes of patients in each study group. The standardized difference will be used as a parameter to quantify the between-group differences for each clinical attribute. This is metric is commonly used in studies utilizing secondary health data, in which a standardized difference of larger than 0.1 indicates a meaningful difference with respect to the clinical attribute between the two study groups.

For the analysis of primary outcome, the incidence rates of AEs during entire followup period will be calculated based on the following formula:

NIS Protocol Page 26 of 43 BI Study Number: 1237-0109 c38644780-01

Proprietary confidential information © 2022 Boehringer Ingelheim International GmbH or one or more of its affiliated companies

(Total number of patients in the Tio+Olo cohort experiencing an event of interest for the first time during the given time period) / (Total person-time at risk from current use of Tio+Olo during the given period)

For the analysis of the primary outcome, individuals will be followed up from the index date until the earliest of the date of the follows, whichever occurs first 1) disenrollment; 2) the end of the study period; 3) death; 4) discontinuation of the index drug; 5) adding ICS mono on top of Tio/Olo.

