7.2 OUTCOMES

7.2.1 Primary outcomes

➤ Incidence rate of adverse events in patients with COPD treated with Tio+Olo

List of adverse events:

For acute, potentially recurrent events, including COPD exacerbations listed below, all subjects will be evaluated, regardless of whether such events occurred during the one-year baseline period.

- Respiratory tract disorders
 - 1. Nasopharyngitis
 - 2. Pneumonia
 - 3. COPD exacerbation
- Gastrointestinal disorders
 - 1. Constipation
 - 2. Diarrhoea
- Urinary disorders
 - 1. Urinary retention
 - 2. Urinary tract infection
- Immune system
 - 1. Urticaria

Statistical and Epidemiological Analysis Plan (SEAP) for Non-Interventional Studies (NIS) Template

c40431892-01 Page 10 of 38

Proprietary confidential information © 2022 Boehringer Ingelheim International GmbH or one or more of its affiliated companies

2. Rash

For chronic conditions listed below, subjects who had diagnosis of the condition during the one-year baseline period will be excluded from the incidence of adverse event analysis.

- Cardiovascular disorders
 - 1. Arrhythmia
 - 2. Myocardial ischemia
 - 3. Supraventricular tachycardia
- Ophthalmic disorders
 - 1. Glaucoma
- Serious Adverse Event (SAE)
 - 1. Nonfatal myocardial infarction
 - 2. Nonfatal stroke (hemorrhagic stroke, ischemic stroke and acute cerebrovascular disease)

Lastly, all-cause mortality, a serious adverse event, will be evaluated.

Relevant ICD codes and operational definition are provided in the Annex.

[figure not shown]
For the analysis of the primary outcome, individuals will be followed up from the index date until the earliest of the following

- 1) Outcome of interest
- 2) disenrollment;
- 3) the end of the study period;
- 4) death;
- 5) discontinuation of the index drug use as a lapse of 45 days without subsequent prescription;
- 6) adding ICS mono on top of Tio/Olo.

Statistical and Epidemiological Analysis Plan (SEAP) for Non-Interventional Studies (NIS) Template

c40431892-01 Page 11 of 38

Proprietary confidential information © 2022 Boehringer Ingelheim International GmbH or one or more of its affiliated companies

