10. DATA ANALYSIS

10.1 MAIN ANALYSIS

All variables, including patient characteristics, baseline measures, and outcomes, will be analyzed descriptively.

- For all analyses, variables will be reported as follows: Continuous variables (e.g., age) will be presented as means (with standard deviation, SD) and/or medians (with interquartile range, IQR), minimum, maximum.
- Categorical variables (e.g., sex) will be presented as absolute and relative frequencies.

We will first describe formation of the study cohort. Patient characteristics at baseline will be described using standard descriptive statistics. Absolute standardized differences (ASDs) will be used to compare the characteristics between the two groups, in which a >0.1 ASD indicates a meaningful difference.

As an objective of the study was to compare the clinical attributes of patients in each study group. The standardized difference will be used as a parameter to quantify the between-group differences for each clinical attribute. This is metric is commonly used in studies utilizing

Statistical and Epidemiological Analysis Plan (SEAP) for Non-Interventional Studies (NIS) Template

c40431892-01 Page 15 of 38

Proprietary confidential information © 2022 Boehringer Ingelheim International GmbH or one or more of its affiliated companies

secondary health data, in which a standardized difference of larger than 0.1 indicates a meaningful difference with respect to the clinical attribute between the two study groups.

For the analysis of primary outcome, the incidence rates of AEs during entire follow-up period will be calculated based on the following formula:

(Total number of patients in the Tio+Olo cohort experiencing an event of interest for the first time during the given time period) / (Total person-time at risk from current use of Tio+Olo during the given period)

[figure not shown]
Number of at-risk patients will be defined for specific adverse outcome of interest, taking into account whether it is a chronic condition for which patients with a prevalent condition are not considered at risk.

For the analysis of the primary outcome, individuals will be followed up from the index date until the earliest of the following

- 1) Outcome of interest
- 2) disenrollment;
- 3) the end of the study period;
- 4) death;
- 5) discontinuation of the index drug use as a lapse of 45 days without subsequent prescription;
- 6) adding ICS mono on top of Tio/Olo.

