ANNEX 1. ADDITIONAL INFORMATION

Table 1. Demographic and cohort entry of the Tio/Olo cohort and LAMA/LABA cohort

	Tio/Olo cohort N=xxxx		LAMA/LABA coho N=xxxx	
	N	%	N	%
Gender				
Male				
Female				
Age				
Mean, SD				
40~59				
60~79				
80+				
Calendar year of cohort entry				
2014				
2015				
2016				
2017				
2018				
2019				
Season of cohort entry date				
Spring (Mar-May)				
Summer (Jun-Aug)				
Fall (Sep-Nov)				
Winter (Dec-Feb)				

Statistical and Epidemiological Analysis Plan (SEAP) for Non-Interventional Studies (NIS) Template

c40431892-01 Page 20 of 38

Table 2. Incidence rate of adverse events in patients with COPD treated with Tio+Olo

Adverse event	No. of events	Person-Years	Incidence rate (per 100 000 person year)	95% CI
Potentially recurrent events				
Nasopharyngitis				
Pneumonia				
Moderate COPD exacerbation				
Severe COPD exacerbation				
Constipation				
Diarrhoea				
Urinary retention				
Urinary tract infection				
Urticaria				
Rash				
Incident events (no occurrence o	f corresponding	g codes during t	the 1-year baselin	ie period)
Arrhythmia				
Myocardial ischemia				
Supraventricular tachycardia				
Glaucoma				
Nonfatal myocardial infarction				
Nonfatal hemorrhagic stroke				
Nonfatal ischemic stroke				
Nonfatal Acute, but ill-				
defined, cerebrovascular				
disease				
Death				

Statistical and Epidemiological Analysis Plan (SEAP) for Non-Interventional Studies (NIS) Template

c40431892-01 Page 21 of 38

Table 3. Secondary outcome (baseline comparison between two study groups)

- ,		1			J & 1)
	Tio/Ol/	o cohort	LAM	A/LABA	
		XXXX	со	hort	Standardized
			N=	XXXX	difference
	N	%	N	%	
COPD treatments in 1 year prior to inde	ex date				
LAMA					
LABA					
ICS					
ICS+LABA free combination					
ICS+LAMA free combination					
LAMA+LABA free combination					
ICS+LAMA+LABA free combination					
ICS/LABA FDC					
LAMA/LABA FDC					
ICS/LAMA/LABA FDC					
Use of other respiratory drugs in 1 year	prior to	index			
date					
Mucolytics					
Theophylline					
Short-acting beta-agonists (SABA)					
Short-acting muscarinic antagonists					
(SAMA)					
Acute COPD exacerbation in 1 year prior	or to inde	x date			
Moderate exacerbation					
0					
1					
>=2					
Severe exacerbation					
0					
1					
>=2					
All exacerbations (Moderate +					
Severe)					
0					
1 >=2					
	c prior to	indov			
Acute COPD exacerbation in the 30 day date	s prior to	inuex			
Moderate exacerbation					
0 1					
>=2					

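### Table 1's confidence intervals assume 12,000 patient-years with no on-treatment censoring, and its exacerbation row needs 6,650 events from at most 4,000 countable patients

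*Protocol*

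**What the plan says.** **Precision.** Protocol section 9.5 takes published incidence rates for four events, assumes that "4000 patients were enrolled in the study in a uniform distribution from 0 to 6 years", and tabulates Poisson-based 95% limits with N = 4000 in every row. The abstract repeats the table ("The following table provides an estimation and 95% CI for incidence rate of each AE").

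**Estimator.** Protocol section 9.7.1 and SAP section 10.1 define the incidence rate with this numerator: "Total number of patients in the Tio+Olo cohort experiencing an event of interest for the first time during the given time period". The denominator is "Total person-time at risk from current use of Tio+Olo during the given period". In both documents follow-up ends at disenrollment, study end, death, discontinuation or addition of ICS monotherapy. SAP sections 7.2.1 and 10.1 add the outcome itself as a stopping point and define stopping treatment as "discontinuation of the index drug use as a lapse of 45 days without subsequent prescription".

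**At-risk set.** For chronic conditions, which include arrhythmia and supraventricular tachycardia (SVT), SAP section 7.2.1 states that "subjects who had diagnosis of the condition during the one-year baseline period will be excluded from the incidence of adverse event analysis". SAP section 10.1 adds: "Number of at-risk patients will be defined for specific adverse outcome of interest".

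**Reporting.** SAP Annex 1, Table 2 has one row for "Moderate COPD exacerbation" and another for the severe form. Protocol Table 1 has a single pooled row.

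**The concern.** The table that states the expected precision of the primary outcome appears to describe a different quantity from the one the study will estimate. Uniform entry over six years with no early censoring gives an average of three years at risk per patient. An on-treatment, first-event rate must accumulate less person-time than that. In the exacerbation row, the implied count also exceeds the number of patients who can contribute to the numerator.

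No hypothesis is tested and no precision target is set, so neither power nor type I error is at stake. But expected precision is what a descriptive safety study has to offer at the planning stage, and Table 1 is the only such statement in the visible text. A reader relying on it would expect narrower intervals than the planned analysis can give.

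**Working it through.** **1. Reproducing Table 1.** Inputs from Protocol 9.5: N = 4,000, entry uniform over 0 to 6 years, and the tabulated rates. Mean follow-up is 3 years, so PY = 4,000 × 3 = 12,000. Expected events = rate × 12,000 / 100. The limits are the 2.5% and 97.5% points of that Poisson count, divided by PY.

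| Event | Rate per 100 PY | Expected events | Poisson points | Limits per 100 PY | Printed |
|---|---|---|---|---|---|
| Pneumonia | 4.69 | 562.8 | 517, 610 | 4.308, 5.083 | same |
| COPD exacerbation | 55.42 | 6,650.4 | 6,491, 6,811 | 54.092, 56.758 | same |
| Arrhythmia | 1.82 | 218.4 | 190, 248 | 1.583, 2.067 | same |
| SVT | 1.16 | 139.2 | 117, 163 | 0.975, 1.358 | same |

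The protocol does not print 12,000 PY, but the match is exact. With 24,000 PY (six years for everyone) the pneumonia limits would be 4.417 to 4.967, which do not match.

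**2. Exacerbation row, no persistence assumption.** The numerator cannot exceed 4,000, yet the row implies 6,650. If all 12,000 PY stayed in the denominator, the rate could be at most 4,000 / 12,000 = 33.3 per 100 PY. The relative half-width is at least 1.96 / √4,000 = 3.10%, or 0.0310 × 55.42 = 1.72 per 100 PY at the tabulated rate. Table 1 implies (56.758 − 54.092) / 2 = 1.33, which is 2.4%.

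**3. First event over on-treatment time.** With first-event rate λ and discontinuation rate d, both constant per year:

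PY = 4,000 × ∫₀⁶ (1 − t/6) exp(−(λ + d)t) dt; events = λ × PY; half-width = 1.96 × √events / PY.

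The values of d are assumptions: 0 (nobody stops) and 1/3, 0.5, 1 and 2, which correspond to mean times on treatment of 36, 24, 12 and 6 months. Each cell gives events / PY, then the half-width per 100 PY.

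| Event (stated half-width) | d = 0 | 36 months | 24 months | 12 months | 6 months |
|---|---|---|---|---|---|
| Pneumonia (0.39) | 514 / 10,949; 0.41 | 299 / 6,380; 0.53 | 242 / 5,169; 0.59 | 151 / 3,214; 0.75 | 84 / 1,795; 1.00 |
| Arrhythmia (0.24) | 211 / 11,575; 0.25 | 121 / 6,638; 0.33 | 97 / 5,347; 0.36 | 60 / 3,287; 0.46 | 33 / 1,818; 0.62 |
| SVT (0.19) | 136 / 11,726; 0.195 | 78 / 6,701; 0.26 | 63 / 5,390; 0.29 | 38 / 3,304; 0.37 | 21 / 1,824; 0.49 |
| Exacerbation (1.33) | 2,840 / 5,125; 2.04 | 2,031 / 3,665; 2.41 | 1,771 / 3,196; 2.58 | 1,273 / 2,298; 3.04 | 811 / 1,464; 3.81 |

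First-event counting alone (d = 0) widens pneumonia by 5%, arrhythmia and SVT by 2%, and exacerbation by 53%. With discontinuation, the first three rows are about 1.35, 1.5, 1.9 and 2.6 times the stated width, and exacerbation about 1.8, 1.9, 2.3 and 2.9 times.

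**4. If 55.42 is a recurrent-event rate.** The protocol does not say which kind of rate it is. Assume gamma frailty with variance 0.5, 1 or 2 and no discontinuation.

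| Frailty variance | First events / PY | Rate per 100 PY | Half-width | Relative half-width |
|---|---|---|---|---|
| 0.5 | 2,498 / 5,933 | 42.1 | 1.65 | 3.9% |
| 1 | 2,238 / 6,531 | 34.3 | 1.42 | 4.1% |
| 2 | 1,876 / 7,369 | 25.5 | 1.15 | 4.5% |

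With variance 2 and a 36-month mean time on treatment, there are 1,390 first events over 4,632 PY, and the half-width is 1.58.

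**5. Baseline exclusions.** Removing a proportion p of patients widens an interval by 1/√(1 − p). For assumed p of 5%, 10% and 20% the factors are 1.026, 1.054 and 1.118, applying to arrhythmia and SVT only.

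**The case against.** The strongest reply concerns exacerbation. If 55.42 is a recurrent rate, the first-event rate is lower and absolute precision before discontinuation is close to the stated 1.33: 1.65, 1.42 or 1.15 in step 4, the last of them narrower. Likewise, the protocol's own stopping list does not end follow-up at the outcome. Under that list the limiting case of 4,000 events over 12,000 PY has a half-width of 0.0310 × 33.3 = 1.03. This stands as a limit on the claim: the 1.72 bound holds only at a rate of 55.42. Relative precision is still worse than stated in every case, and at variance 2 a 36-month mean time on treatment already takes the half-width above 1.33.

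SAP Table 2 groups exacerbations under potentially recurrent events and has a column for number of events, which might suggest recurrent counting. However, SAP 7.2.1 uses recurrence to decide who is at risk despite baseline events, while the formula counts patients and the SAP stops follow-up at the outcome.

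SAP 7.2.1 lists exacerbation as one outcome, so a pooled planning row is defensible. The moderate and severe split is a matter of presentation, not an arithmetic error.

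Finally, the sample is whatever the database holds, Table 1 is conditional on published rates being replicated, and the final report will show observed intervals. That limits the consequence but does not make the planning figures right.

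**Conclusion.** The point holds and should be fixed. Table 1 rests on 12,000 PY with no early censoring, and its intervals do not describe the first-event, on-treatment rate defined in Protocol 9.7.1 and SAP 10.1.

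The impossibility of 6,650 countable events, and a relative half-width of at least 3.1% against 2.4%, need no persistence assumption. For pneumonia, arrhythmia and SVT the implied counts are feasible. At the tabulated rates the direction of the error is certain, because censoring can only remove person-time.

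The size is conditional. The multiples of about 1.35 to 2.6 (1.8 to 2.9 for exacerbation) assume exponential persistence with a mean of 36 to 6 months, and the exacerbation multiples also treat 55.42 as a constant first-event rate. Baseline exclusions add 3% to 12% for arrhythmia and SVT under assumed prevalences of 5% to 20%. The consequence is confined to overstated planning precision.

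**What to change.** Keep the 4,000 patients and the estimator. In Protocol 9.5 and the abstract copy:

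- Recompute each row from expected first events over event-free, on-treatment person-time, across a stated range of assumed persistence (for example, means of 6 to 36 months), and print the expected events and person-years.
- State whether the cited exacerbation rate is taken as first-event or recurrent and, if recurrent, how it is converted.
- Use a stated at-risk number below 4,000 for arrhythmia and SVT, to reflect the SAP's baseline exclusions.
- Optionally, if separate rates are available, give moderate and severe exacerbation their own rows to match SAP Table 2.

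The cost is a short calculation and one table replaced in two places. The stated precision becomes less favourable. No further patients or data are needed, and the cohort does not change.

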9.6 DATA MANAGEMENT

Full details of the data management plan are documented in a separate NIS-Data Management and Review Plan (NIS-DMRP).

9.7 DATA ANALYSIS

Full details of the statistical analysis will be documented in the SEAP, which will be finalized before the end of data collection.

9.7.1 Main analysis

All variables, including patient characteristics, baseline measures, and outcomes, will be analysed descriptively.

- For all analyses, variables will be reported as follows: Continuous variables (e.g., age) will be presented as means (with standard deviation, SD) and/or medians (with interquartile range, IQR), minimum, maximum.
- Categorical variables (e.g., sex) will be presented as absolute and relative frequencies.

We will first describe formation of the study cohort. Patient characteristics at baseline will be described using standard descriptive statistics. Absolute standardized differences (ASDs) will be used to compare the characteristics between the two groups, in which a >0.1 ASD indicates a meaningful difference.

As an objective of the study was to compare the clinical attributes of patients in each study group. The standardized difference will be used as a parameter to quantify the between-group differences for each clinical attribute. This is metric is commonly used in studies utilizing secondary health data, in which a standardized difference of larger than 0.1 indicates a meaningful difference with respect to the clinical attribute between the two study groups.

For the analysis of primary outcome, the incidence rates of AEs during entire followup period will be calculated based on the following formula:

NIS Protocol Page 26 of 43 BI Study Number: 1237-0109 c38644780-01

Proprietary confidential information © 2022 Boehringer Ingelheim International GmbH or one or more of its affiliated companies

(Total number of patients in the Tio+Olo cohort experiencing an event of interest for the first time during the given time period) / (Total person-time at risk from current use of Tio+Olo during the given period)

For the analysis of the primary outcome, individuals will be followed up from the index date until the earliest of the date of the follows, whichever occurs first 1) disenrollment; 2) the end of the study period; 3) death; 4) discontinuation of the index drug; 5) adding ICS mono on top of Tio/Olo.

